6.0 STUDY RATIONALE

Given the significant QOL impact of nasal obstruction, it is important to measure not only the physical symptoms (congestion, obstruction and ability to breathe) but also the impact of those symptoms on the patient's ability to sleep and the related consequences on rest, productivity, concentration and ability to participate in the normal daily activities of work and life.

In addition to the physical benefits of increased nasal patency, there are significant quality of life benefits that are associated with better breathing. After correcting nasal obstruction patients report significantly better sleep function (e.g. better night's sleep; waking up during the night and difficulty falling asleep) as well as better psychological function (e.g. concentration, productivity and frustration). (Brown, Hopkins, et. al). We believe that these benefits may well be durable beyond the initial six months of the study in terms of sustained quality of life impact.

The purpose of this study is to continue to evaluate additional subjects for treatment with the Vivaer[®] ARC Stylus for up to 36 months post-procedure.

7.0 SUMMARY DEVICE DESCRIPTION

The System is comprised of the Vivaer[®] ARC Stylus (Figure 7, Figure 8) which is a disposable handheld device capable of delivering bipolar radiofrequency energy to tissue, and the Aerin Console, a FDA cleared generator (K162810) with temperature control capable of delivering very low doses of energy (Figure 9). The Aerin Console with the Vivaer[®] ARC Stylus (Figure 9) make up the Vivaer[®] System.

The Vivaer[®] ARC Stylus is a cleared device (K172529) and consists of a handle, shaft and treatment tip. An array of bipolar electrodes is positioned on a non-conductive tip which is attached to a handle via a non-conductive shaft. A temperature sensor is located on the tip to monitor tissue temperature. The Stylus is attached to a temperature-controlled radiofrequency generator via a flexible cable. The Vivaer[®] ARC Stylus temporarily inserted into the nose to access the treated area. It modifies the soft tissues of the nasal airway through the use of low doses of radiofrequency energy. The low-power radiofrequency generates heat within the submucosal tissue, creating a localized lesion. As the lesion heals, the tissue retracts and stiffens. This decreases the nasal airflow resistance thereby improving inflow of air through the nose.

The procedure requires local anesthesia only. The Stylus is manufactured and supplied by Aerin Medical and may be used to treat both nostrils of the patient.

[figure not shown]

Figure 7. Vivaer[®] ARC Stylus

[figure not shown]

Figure 8. Vivaer[®] ARC Stylus Tip

[figure not shown]

Figure 9. Aerin Console with Vivaer® ARC Stylus

8.0 STUDY DESIGN AND ENROLLMENT

8.1 Study Design and Objectives

A Prospective, Multicenter Study of the Aerin Medical Vivaer® ARC Stylus for Nasal Airway Obstruction. The primary objective of this study is to continue to evaluate the effectiveness of the Vivaer® ARC Stylus for treating the nasal valve area to improve symptoms in those diagnosed with nasal airway obstruction.

8.2 Subject Population

The population being approached for this study are male and female subjects who present with symptoms associated with nasal airway obstruction and meet the protocol eligibility criteria.

Eligible subjects must meet the inclusion and exclusion criteria described in Sections 8.3 and 8.4.

Up to 125 treated patients will be enrolled in the study at up to 20 sites in the United States.

8.3 Inclusion Criteria

To be eligible to participate in this clinical investigation, a patient must meet all of the following criteria:

1. Age 18 or older
2. Willing and able to provide informed consent
3. Willing and able to comply with the study protocol
4. Seeking treatment for nasal obstruction
5. NOSE score of ≥ 60 at Baseline
6. Nasal valve is a primary or significant contributor to the subject's nasal obstruction as determined by the study investigator (based on clinical presentation, physical examination, nasal endoscopy, etc.) and the subject has a positive response to any of the following temporary measures (based on patient history or office exam):

- Use of external nasal dilator strips (e.g., Breathe Right Strips)
- Q-Tip test (manual intranasal lateralization)
- Use of nasal stents
- Cottle Maneuver (manual lateral retraction of the cheek)

8.4 Exclusion Criteria

A patient who meets any of the following criteria is not eligible to participate in the study:

1. Prior surgical treatment of the nasal valve
2. Rhinoplasty, septoplasty, inferior turbinate reduction or other surgical nasal procedures within the past three (3) months
3. Anatomy that requires an adjunctive surgical nasal procedure on the same day or 3 months after the Vivaer procedure
4. Medical conditions which in the opinion of the treating physician would predispose the subject to poor wound healing or increased surgical risk.

9.0 STUDY PHASES

The study will be conducted in five phases:

Phase 1: Enrollment (Screening & Consent)

Phase 2: Vivaer[®] Treatment

Phase 3: Investigator Assessment and Subject Follow-Up, Questionnaires (QOL, NOSE and VAS) scales at 3 months

Phase 4: Subject Follow-up Questionnaires (NOSE and QOL) at 6, 12, 24 and 36 months

Phase 5: Study Exit

Study Assessments are defined in Section 9.6.

9.1 PHASE 1: ENROLLMENT (Screening & Consent)

The treating physician or designated research staff will perform a formal evaluation of the study candidate for study eligibility, which may include a history and physical examination of the nasal area, review of overall medical history, understanding of general health and discussion of any conservative measures used for nasal airway obstruction.

The following data will be collected:

- Patient demographics
- Medical history including prior medication use, tests and treatments for nasal airway obstruction
- NOSE Score
- Treating physician pre-treatment visual assessment of the area to be treated
- Photographs/videos of each nostril will be captured

The investigator or designated staff will review all aspects of the study with the patient including the protocol, associated documents, and the follow-up process. Once the study has been explained and any questions have been answered the patient will complete and sign the Informed Consent Form (ICF).

The initial consent process as well as re-consent, when required, may take place in person or remotely (e.g., via telephone or other remote platforms such as video conferencing used in compliance with site policy) per the discretion of the investigator and with the agreement of the subject/consent designee. Whether in person or remote, the privacy and confidentiality of the subject will be maintained. The person explaining consent (and subject/consent designee, when in person) will be located in a private area (e.g., clinic consult room).

When consent is conducted remotely, the subject/consent designee will be informed of the private nature of the discussion and will be encouraged to relocate to a more private setting if needed. The subject should be informed of approximately how long the process will take and what information will be presented. The subject and person explaining consent will view individual copies of the approved consent document on screens at their respective locations; the same screen may be used when both the person explaining consent and the subject are co-located but this is not required. When remote, consent will be documented with required signatures on the electronic document. When an electronic document with a digital signature is used for the documentation of consent, this study will use the Adobe Acrobat platform, which is 21 CFR Part 11 compliant to obtain the required signatures. The identity of the subject will be determined by a prompt, which will require the provision of information from an official identification document and to answer security questions, prior to obtaining the signature. An electronic signature with a timestamp will be provided by the required parties through system prompts. Both the person explaining informed consent and the subject must sign the electronic document.

Whether the consent is obtained from the subject in person or remotely, the consent process must provide sufficient opportunity for the subject to consider whether to participate and to ask questions. A copy (paper or electronic) of the signed and dated consent must be provided to the subject.

9.2 PHASE 2: VIVAER[®] TREATMENT

Subjects will have their nasal valve treated in a single Vivaer[®] treatment session and will be considered enrolled once the device has entered the nasal cavity. The procedure will be performed in accordance to its intended use. The area planned for treatment will be visually assessed by the physician immediately before and after the treatment session. Subjects should be scheduled for Vivaer treatment within 30 days after their baseline assessment.

The following data will be collected:

- Physician Physical Examination of the Nasal Area
- Treatment Information
- Endoscopic Nasal Examination
- Photographs/videos of each nostril will be captured
- Evaluate Treatment Adverse Events

The follow-up period will begin after the study treatment session.

9.3 PHASE 3: INVESTIGATOR ASSESSMENT AND SUBJECT FOLLOW-UP AT 3 MONTH

The following data will be collected at the 3 month clinic visit:

- Physician Physical Examination of the Nasal Area
- Endoscopic Nasal Examination
- Photographs/videos of each nostril will be captured
- Evaluate for any Adverse Events

Study subjects will be asked to complete the following self-reported questionnaires:

- NOSE Score
- Quality of Life (QOL) Questionnaire
- Visual Analog Scale (VAS) for Pain related to the treated area

9.4 PHASE 4: SUBJECT FOLLOW-UP QUESTIONNAIRES AT 6, 12, 24 and 36 MONTHS

Subjects will be contacted for follow-up data collection at **6, 12, 24 and 36 months** calculated from the treatment date.

Study subjects will be asked to complete the following self-reported questionnaires:

- NOSE Score
- Quality of Life (QOL) Questionnaire

If any changes in medication, health status or subject received another nasal procedure, the subject will be instructed to contact the study staff.

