Assessments	Prior to Nasal Valve Treatment	Nasal Valve, Treatment	Investigator Visual Assessment & subject follow-up at 3 months (+/- 2 weeks)	6, 12, 24 and 36 month Follow-ups (+/- 1 month)
Demographics and Medical History	X			
Nasal Evaluation	X	X	X	
Medication Review	X	X	X	X
Visual Assessment of Treatment Area & Photographs/videos	X	X	X	
Vivaer ARC Stylus Treatment		X		
NOSE Score	X		X	X
Visual Analog Scale (VAS)			X	
Subject QOL Questionnaire			X	X
Adverse Event Review		X	X	X
Study Exit				X*

*At 36 month visit

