10.0 ADVERSE EVENTS AND PRODUCT COMPLAINTS

10.1 Adverse Events

Adverse events (AEs) may occur during the treatment phase or during the follow-up phase. Adverse events occurring after the baseline assessment but before the treatment procedure will be documented in the subject's medical record but will not count as related to the study device or procedure.

Each adverse event will be recorded in the corresponding subject's CRF. Each adverse event will be judged by the Investigator as to its relationship and level of relatedness to the study device and/or study procedure. In addition, the Investigator will identify the date of onset, severity and duration of the AE. All adverse events will be monitored until they are adequately resolved or explained. If a subject reaches the 36 month follow-up visit and is experiencing a new or ongoing adverse event, the study sponsor should be contacted to discuss the need and/or methods for continued surveillance of the event.

The Investigator must submit to the Sponsor a report of any Serious Adverse Event (SAE), Serious Adverse Device Effect (SADE) or Unanticipated Adverse Device Effect (UADE) within 24 hours of knowledge of the event.

Sponsor Contact: [name], MSN, MPH
[contact]
Email: [contact]

In addition, the Investigator will report adverse events to the reviewing IRB / EC (as applicable) according to the local reporting requirements.

Adverse Events

Adverse Event (AE) – any untoward medical occurrence in a subject (ISO 14155).

NOTE: This definition does not imply that there is a relationship between the adverse event and the device under investigation.

Serious Adverse Event (SAE) – an adverse event that (ISO 14155):

- led to a death,
- led to a serious deterioration in the health of the subject,
- resulted in a life-threatening illness or injury,
- resulted in a permanent impairment of a body structure or a body function,
- required hospitalization or prolongation of existing hospitalization,
- resulted in medical or surgical intervention to prevent permanent impairment to body structure or function,
- led to fetal distress, fetal death, a congenital abnormality, or birth defect.

Adverse Device Effect (ADE) – any untoward and unintended response to a medical device (ISO 14155)

NOTE: This includes any event resulting from insufficiencies or inadequacies in the instructions for use or the deployment of the device. This definition also includes any event that is a result of user error.

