16.0 DATA COLLECTION

Subject data will be collected in a secure electronic data capture (EDC) system via the internet. All baseline, index procedure and 3-month data will be entered by the study site personnel in the electronic Case Report Forms (eCRFs). A unique subject ID number will be assigned to each subject. Every reasonable effort should be made to complete data entry within 10 business days of data collection. Any discrepancies may be queried during routine monitoring visits. Data monitoring will be performed to verify data accuracy and ensure queries are resolved.

Subject reported outcomes obtained via EDC system are considered to be source documents for this study.

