4 STUDY OBJECTIVES AND ENDPOINTS

The primary objective of this study is to continue to evaluate the effectiveness of the Vivaer ARC Stylus for treating the nasal valve area to improve symptoms in those diagnosed with NAO. Effectiveness is assessed through several outcome measures and endpoints as described in Table 1. Outcome measures are further described in Section 8.

Statistical Analysis Plan TP900 (AERWAY)

Table 1. Objectives and endpoints.

Objective	Outcome measures and Endpoints
Evaluate effectiveness through symptom improvement.	
Nasal Obstruction Symptom Evaluation (NOSE) Scale score:
 
 • Mean and mean change from baseline at the 3-, 6-, 12-, 24-, and 36-month follow-up evaluations. • Distribution of NOSE Scale score severity categories (mild, moderate, severe, extreme) at the 3-, 6-, 12-, 24-, and 36-month follow-up evaluations. • Mean, change from baseline in mean, and response distribution of the 5 components of the NOSE Scale score (nasal congestion, nasal blockage, trouble breathing, trouble sleeping, and getting enough air during exercise) at the 3-, 6-, 12-, 24-, and 36-month follow-up evaluations. • Proportion of responders based on improvement in NOSE Scale score at the 3-, 6-, 12-, 24-, and 36-month follow-up evaluations.
Evaluate effectiveness through participant quality of life (QoL) questionnaire feedback.	
QoL questionnaire
 
 • Item response distributions and means where appropriate, at the 3-, 6-, 12-, 24-, and 36-month follow-up evaluations.
Evaluate safety through the safety profile.	
Adverse events
 
 • Frequency of device-related and procedure-related serious adverse events through the 3-month evaluation • Incidence (type, severity, relatedness) of adverse events overall and by follow-up interval.
Evaluate Other Exploratory Outcome Measures	
Nasal Assessment
 
 • Item response distributions prior to the procedure, immediately after the procedure, and at 3 months after the procedure. 
Visual analog scale (VAS) for pain
 
 • VAS pain score assessed at 3 months. 
Medications
 
Updates to current medications or any new or changed medications at the 3-, 6-, 12-, 24-, and 36-month follow-up evaluations.

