8.4 Participant Quality of Life Assessment

The QoL questionnaire consists of 4 parts (Appendix A). The first part has 24 items and asks the participant to rate how much of a problem various symptoms and potential effects of their nasal obstruction present to their quality of life at the time of taking the survey relative to the time prior to having the Vivaer procedure. A 6-point ordered rating scale is used with descriptors:

- No Problem (0)
- Very Mild Problem (1)
- Mild or Slight Problem (2)
- Moderate Problem (3)
- Severe Problem (4)
- Problem as bad as it can be (5).

The second part has 3 questions related to frequency of use of medical products for nasal obstruction symptom relief now compared to before the procedure. Responses are on a 5-point ordered rating scale with descriptors:

- Much less frequently
- Less frequently
- About the same
- More frequently
- Much more frequently.

There is also a response of not applicable if a product was not being used prior to the procedure.

Statistical Analysis Plan TP900 (AERWAY)

The third part has 3 questions. The first is a rating on a 10-point scale of satisfaction with symptom relief following the procedure where 1 represents symptoms have no effect on daily activity and 10 being symptoms completely prevent daily activity. The second question asks if the procedure would be recommended to a friend with similar symptoms (yes or no) and the third question asks if symptoms returned would you undergo the procedure again (yes/no).

The fourth section requests information on general health, including undergoing additional nasal surgery, significant changes in health, and changes to medication regimen.

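### Protocol 9.4 omits the adverse event and medication reviews that the schedule requires at 6 to 36 months, so late adverse events may be collected unevenly and under-recorded

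*Protocol*

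**What the plan says.** Protocol 9.4 governs the 6-, 12-, 24- and 36-month contacts. It says "Study subjects will be asked to complete the following self-reported questionnaires" and names two, the NOSE and the QoL. It then says "If any changes in medication, health status or subject received another nasal procedure, the subject will be instructed to contact the study staff". The Phase 4 line in Protocol 9.0 names the same two instruments.

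The schedule of assessments, Protocol Table 1, has a row "Adverse Event Review" that is marked at treatment, at 3 months and in the 6-to-36-month column. Its medication review row is also marked in that late column.

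The text for the 3-month visit (Protocol 9.3) includes "Evaluate for any Adverse Events", and 9.2 has a similar item for the treatment visit.

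On data flow, Protocol 16.0 says "All baseline, index procedure and 3-month data will be entered by the study site personnel". It names no one for later data. Protocol 10.1 requires serious events to be reported "within 24 hours of knowledge of the event".

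SAP 8.4 describes part 4 of the QoL questionnaire: "The fourth section requests information on general health, including undergoing additional nasal surgery, significant changes in health, and changes to medication regimen". The safety endpoints in SAP Table 1 include "Incidence (type, severity, relatedness) of adverse events overall and by follow-up interval", and SAP 9.10 adds a time course of AEs.

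**The concern.** Sites have two different instructions for the same contacts. A site working from the schedule asks about AEs at every late contact. A site working from 9.4 collects two questionnaires and relies on the subject to report changes. Nothing in the documents would show an analyst which was done.

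AE incidence by follow-up interval and the time course compare periods with each other. That comparison is sound only if events are sought in the same way throughout. If the method changes at 3 months, part of any later fall in the recorded rate comes from the method and could be read as long-term safety.

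Timing is also at stake. The 24-hour reporting period runs from the investigator's knowledge, so a serious event that sits in an unreviewed questionnaire would be reported late.

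The same channel feeds the medication-change summaries in SAP 9.8. It also feeds the rule there that removes efficacy data collected after a further ENT procedure.

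**Working it through.** The plan states no AE rate, capture rate or power figure for this period, so there is no figure to reproduce. The check compares the texts.

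**Step 1: what each text requires.**

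| Contact | AE review in phase text | Medication review in phase text | AE review in Protocol Table 1 | Medication review in Protocol Table 1 |
|---|---|---|---|---|
| Treatment | Yes (9.2) | Not listed | Yes | Yes |
| 3 months | Yes (9.3) | Not listed | Yes | Yes |
| 6, 12, 24, 36 months | Not listed (9.4) | Not listed; subject told to contact staff | Yes | Yes |

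For AEs, phase text and schedule agree up to 3 months and disagree at every contact after that.

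**Step 2: does Protocol 9.6 resolve it?** It says subjects will be asked about adverse experiences and medications. It also ties the timing of its assessments to the phase descriptions, and Phase 4 names no AE review. Table 1 sits within 9.6 and says the opposite, so the conflict stays open.

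**Step 3: which active prompts exist after 3 months?** QoL part 4 is one, because the QoL is given at every late contact. SAP 8.5 has medication updates requested at each evaluation, SAP 8.6 says participants are queried about AEs, and SAP 3 describes the late evaluations as telephone contacts. Part 4 is not described as recording onset, severity or relatedness. Appendix A as available for this review shows only the first three parts, so the wording of part 4 could not be checked.

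**Step 4: is there a route from a late answer to an AE record?** Protocol 10.1 requires each AE to be recorded and judged by the investigator, including during follow-up. Protocol 16.0 names site entry for baseline, procedure and 3-month data and is silent on later data. Protocol 12.1 describes an electronic questionnaire system, whereas SAP 3 describes telephone contact. No text says who reads a part 4 answer, when, or how it becomes an AE form.

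**Step 5: how much of follow-up is affected.**
- Contacts: 4 of 5 post-treatment contacts = 80%.
- Time: (36 − 3)/36 = 33/36 = 91.7%.
- Maximum person-time with 125 participants and full retention: 125 × 33/12 = 343.75 person-years.

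**Step 6: direction of the effect.** Let c be the fraction of late events that is captured. Then recorded rate = true rate × c. If the Table 1 review is done as fully as before month 3, the method adds no distortion between intervals. If it is not done and c falls, the late rate is understated by the fraction 1 − c. As an illustration with assumed inputs, a true late rate of 5% would be recorded as 5.0%, 4.5%, 3.75% or 2.5% at c = 100%, 90%, 75% or 50%. The documents support no particular value of c, so these figures show direction and are not an estimate.

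**The case against.** The strongest reply is that the phase lists are not exhaustive. Sections 9.2 and 9.3 also leave out the medication review that Table 1 marks at treatment and 3 months, and nobody would conclude that it is skipped there. Section 9.4 says subjects will be contacted and does not exclude the scheduled review. This stands. It defeats an inference that a reader might draw, namely that no AE question is asked after 3 months. QoL part 4 and SAP 8.5 and 8.6 count against that inference too.

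The reply does not remove the conflict. For AEs, 9.2 and 9.3 do list the evaluation and 9.4 does not. For changes in health and medication, 9.4 also puts a rule of its own in place, under which the subject takes the initiative.

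A second reply is that a fall in AEs after 3 months may be real, because in the pivotal trial most events occurred within 4 weeks of the procedure (Protocol 5.0). This also stands. It is a reason to keep the method constant, since a real fall and a collection effect otherwise cannot be separated.

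A third is that 10.1 already requires every AE to be recorded and judged. That holds once the site knows of the event. The gap lies before that point.

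A reader might also project missed serious events from the pivotal trial's 2 in 50 subjects over 26 weeks. The documents do not support this. Neither event was related to device or procedure, and any count of missed events needs a capture fraction that would have to be invented.

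**Conclusion.** The inconsistency is real and should be corrected. Section 9.4 and the Phase 4 line in 9.0 omit the AE and medication reviews that Protocol Table 1 requires at 6, 12, 24 and 36 months, and the path from QoL part 4 to an AE form is not described.

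Late ascertainment may therefore vary between sites and differ from that of the first 3 months. AE incidence by interval and the time course may be understated after month 3, and serious event reports may be delayed. Four of five post-treatment contacts and 33 of 36 months are exposed.

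This is a risk that depends on sites following 9.4 as written. To say that late rates will be too low goes further than the documents allow, because sites that follow Table 1 carry out the review. The endpoint of device- and procedure-related serious events through 3 months is not affected: 9.3 and Table 1 agree on that visit.

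**What to change.** - **Protocol 9.4 (and the Phase 4 line in 9.0):** add an AE review and a medication review by site staff at each of the 6-, 12-, 24- and 36-month contacts, covering the period since the last contact. This carries out what Table 1 already requires.
- **Protocol 16.0:** state that site staff review every QoL part 4 response, open an AE form where a health change or procedure is reported, and pass it to the investigator for the judgement required by 10.1.
- **SAP 9.10:** report the ascertainment method for each interval, and do not read a fall after 3 months as lower risk where no review was documented. SAP 3 indicates that some late contacts have already taken place. For those, only this reporting step can help.

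The cost is a few sentences in three places and a few minutes of site staff time at contacts that SAP 3 already describes as telephone calls. The reported late AE count may rise, which would reflect more complete collection.
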